² Screening laboratory tests include: ALT, AST, creatinine (and calculate an estimated glomerular filtration rate (eGFR) the formula used is determined by the sites, but should be consistent throughout the study), and urine or serum pregnancy test for females of child-bearing potential. Laboratory tests performed as part of routine clinical care in the 48 hours prior to enrollment will be accepted for determination of eligibility.

³ Baseline assessments should be performed prior to first infusion. Laboratory tests performed as part of routine clinical care in the 24 hours prior to first dose will be accepted for the baseline safety laboratory tests. Baseline may be the same as the screening laboratory tests if obtained in the 24 hours prior to first dose.

⁴ Safety laboratory tests include WBC with differential, hemoglobin, platelets, creatinine, total bilirubin, ALT, AST, and INR.

⁵ Any laboratory tests performed as part of routine clinical care within the specified visit window can be used for safety laboratory testing. ⁶ In-person visits are preferred but recognizing quarantine and other factors may limit the subject's ability to return to the site for the visit. In this case, the visit may be performed by phone.

- If still hospitalized at Day 15 and 29 or returns for an in-person visit: assess adverse events, collect clinical data, vital signs, safety laboratory tests, and research laboratory samples (OP swab and blood) as able.
- If phone call only on Days 15 and 29 and all Day 22 and Day 60 visits: assess adverse events, clinical status (ordinal scale), readmission to a hospital, and mortality only.

⁷ Oropharyngeal swabs are preferred, but if these are not obtainable, saliva or nasopharyngeal or nasal swabs may be substituted. ⁸ Pre-dose serum sample collections for PK and immunogenicity.

⁹ To include markers of inflammation and coagulation: CRP, ferritin, fibrinogen, d-dimer.

¹⁰ Day 8, 22 and 60 visits performed by phone call or home visit if discharged from the site hospital: assess adverse events, clinical status (ordinal scale), readmission to a hospital, and mortality only.

¹¹ Only collected at selected sites capable of processing.

¹² Steroids and other concomitant therapies intended as specific treatment of COVID-19, as well as all biologics, will be assessed from 7 days prior to enrollment to Day 29. All other concomitant medications will be assessed from 7 days prior to enrollment to Day 15 or upon discharge, whichever comes first.

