3. OBJECTIVES AND ENDPOINTS

Table 3. BET-A Study Objectives

OBJECTIVES	ENDPOINTS (OUTCOME MEASURES)		
Primary			
To evaluate the clinical efficacy of risankizumab relative to the control arm in adults hospitalized with COVID-19 according to clinical status (8-point ordinal scale) at Day 8.	 Not hospitalized, no new or increased** limitations on activities; Not hospitalized, but new or increased limitation on activities and/or requiring new or increased home oxygen, CPAP or BiPAP; Hospitalized, not requiring new or increased supplemental oxygen - no longer requires ongoing medical care; Hospitalized, not requiring new or increased supplemental oxygen - requiring ongoing medical care (COVID-19 related or otherwise); Hospitalized, requiring new or increased supplemental oxygen; Hospitalized, on invasive mechanical ventilation or extracorporeal membrane 		

OBJECTIVES	ENDPOINTS (OUTCOME MEASURES)
	oxygenation (ECMO); 8. Death.
Key Secondary	
1. To evaluate the clinical efficacy of risankizumab as assessed by time to recovery compared to the control arm.	 Day of recovery is defined as the first day on which the subject satisfies 1 of the following 3 categories from the ordinal scale (and does not return to a score of 4 or higher for the remainder of the study period): Not hospitalized, no new or increased limitations on activities; Not hospitalized, but new or increased limitation on activities and/or requiring new or increased home oxygen, CPAP, or BiPAP; Hospitalized, not requiring new or increased supplemental oxygen - no longer requires ongoing medical care.
 To evaluate the proportion of subjects alive and without respiratory failure through Day 29. 	Subjects in ordinal scale 5 or 6 at baseline who did not meet either of the following two categories at any point through Day 29: 7. Hospitalized, on invasive mechanical ventilation or ECMO; 8. Death.
Other Secondary	
 To evaluate the clinical efficacy of risankizumab as compared to the control arm as assessed by: Clinical Severity Ordinal scale: Clinical status using ordinal scale at Days 15 and 29. Time to an improvement of one category and two categories from Day 1 (baseline) using an ordinal scale. Mean change in the ordinal scale from Day 1 to Days 3, 5, 8, 11, 15, 22, and 29. 	• Clinical outcome assessed using ordinal scale daily while hospitalized and on Days 15, 22, and 29.
Oxygenation:Supplemental oxygen use up to Day	• Days of supplemental oxygen (if applicable) up to Day 29.

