8.1.2.1 Measures of Clinical Support, Limitations, and Infection Control

The subject's clinical status will be captured on each study day while hospitalized up until and including Day 29. Once subjects are discharged from the hospital, they will have a study visit on Days 8, 15, 22, 29, and 60 visits (only the ordinal score will be obtained on Day 60) as an outpatient. The Day 8, Day 22 and Day 60 visits do not have laboratory tests or collection of samples and may be conducted by phone. Day 15 and 29 visits are preferred to be in person in order to collect safety laboratory testing, stored samples, and virologic assessments but may be performed. Clinical status is largely measured by the ordinal scale. The ordinal scale can also be evaluated over the phone if the discharged subject is unable to return for in-person visits on Day 15 and 29.

The following measures are recorded for the ordinal scale. See MOP for more detailed description of ventilatory devices in each category:

- Hospitalization.
- Oxygen requirement.
- Non-invasive mechanical ventilation (via mask) requirement.
- High-flow oxygen requirement.
- Invasive mechanical ventilation (via endotracheal tube or tracheostomy tube) requirement.
- ECMO requirement.
- Ongoing medical care preventing hospital discharge (COVID-19 related or other medical conditions).
- Limitations of physical activity (self-assessed and reported as new or increased limitations as compared to status prior to the onset of COVID-19).
- Isolated for infection control purposes.

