3.2. Endpoints

Primary Endpoint

The default primary endpoint is clinical status (8-point ordinal scale) on Study Day 8:

1. Not hospitalized, no new or increased limitations on activities;
2. Not hospitalized, but new or increased limitation on activities and/or requiring new or increased home oxygen, CPAP, or BiPAP;
3. Hospitalized, not requiring new or increased supplemental oxygen - no longer requires ongoing medical care;
4. Hospitalized, not requiring new or increased supplemental oxygen - requiring ongoing medical care (COVID-19 related or otherwise);
5. Hospitalized, requiring new or increased supplemental oxygen;
6. Hospitalized, requiring new or increased non-invasive ventilation or high-flow oxygen devices;
7. Hospitalized, on invasive mechanical ventilation or extracorporeal membrane oxygenation (ECMO);
8. Death.

Key Secondary Endpoints

One of the key secondary endpoints is time to sustained recovery (up to and including Study Day 60) and is defined as the first day on which the subject satisfies 1 of the following 3 categories from the clinical status ordinal scale (and does not return to a score of ≥ 4 up to and including Study Day 60):

1. Not hospitalized, no new or increased limitations on activities;
2. Not hospitalized, but new or increased limitation on activities and/or requiring new or increased home oxygen, CPAP, or BiPAP;
3. Hospitalized, not requiring new or increased supplemental oxygen - no longer requires ongoing medical care.

The other key secondary endpoint is whether the subject did not satisfy one of the following two categories from the ordinal scale up to and including Study Day 29. This analysis will only be completed for those subjects with baseline ordinal score of 5 or 6:

7. Hospitalized, on invasive mechanical ventilation or ECMO;
8. Death.

If the key secondary endpoints are different than what is covered in this master SAP, it will be highlighted for each individual investigational intervention in the corresponding stage-specific appendix.

Other Secondary Endpoints

The other secondary endpoints are:

Efficacy

- Time (days) from Study Day 1 to the first day for which a subject is assessed to be at least 1 category lower (improvement) than the subject's baseline ordinal score up to and including Study Day 60;
- Time (days) from Study Day 1 to the first day for which a subject is assessed to be at least 2 categories lower (improvement) than the subject's baseline ordinal score up to and including Study Day 60;

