Oxygenation, non-invasive ventilation/high flow oxygen, invasive mechanical ventilation/extracorporeal membrane oxygenation (ECMO) will be assessed using results of the 8-point ordinal scale. Hospitalization duration will be assessed using admittance and discharge dates. Mortality will be assessed using results from the electronic case report form (eCRF) serious adverse events (SAEs) form. That is, the number of days from Study Day 1 to the date of death.

Safety will be assessed by the following:

- Cumulative incidence of SAEs up to and including Study Day 60.
- Cumulative incidence of Grade 3 and 4 clinical and/or laboratory AEs up to and including Study Day 60.
- Discontinuation or temporary suspension of study product administration (for any reason).
- Changes in WBC count with differential, hemoglobin, platelets, creatinine, total bilirubin, ALT, AST, eGFR, and INR over time (analysis of lab values in addition to AEs noted above).

Clinical labs will be drawn on Study Days 1, 3, 5, 8, 11 while the subject is hospitalized and on Study Days 15 and 29 if the subject is able to return to the clinic or is still hospitalized.

Exploratory endpoints for post-baseline usage of key concomitant COVID-19 treatments (e.g., steroids) summarized by investigational therapeutic and control arms. The details of analyses for all virology and PK exploratory endpoints will be included in a separate analysis plan(s).

The schedule of study assessments is provided in each stage-specific appendix of the SAP.

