Analysis of time to event endpoints (i.e., sustained recovery, time to improvement, time to mechanical ventilation or death) will be based on observed ordinal score without imputation along with discharge and death information. Refer to Table 7 for additional details regarding censoring and handling of missing data for all endpoints. As handling of missing data might differ for different stages of this study, stage-specific SAPs will provide additional details if handling of missing data for an endpoint for that stage differ from what is in the master SAP.

Table 7: Imputation Method for Each Endpoint and Analysis Type

Endpoint	Analysis	Imputation Method
Primary Endpoint		
1. Ordinal Score at Day 8	Primary	
 • If a subject is discharged from the hospital to another location other than LTAC, hospice care or other hospital, has intermittent missing ordinal score and reported an ordinal score of 1 or 2 after the missing score then: 
 ○ Impute the intermittent missing ordinal score as 1 if the scores reported before and after the missing value are both 1 and no change in oxygen use or hospitalization status after discharge to a location other than hospice, long term acute care or other hospital. ○ Impute the intermittent missing ordinal score as 2 after discharge to a location other than hospice, long term acute care or other hospital if the subject doesn't fall into the category above and subject is not hospitalized at the time point. • LOCF will be used for remaining intermittent missingness of ordinal scores for the next planned assessment. • All missing scores after death will be assigned an ordinal score of 8.

Endpoint	Analysis	Imputation Method
		
 Subjects discharged from the hospital to a location other than LTAC, hospice care or other hospital at their last assessment will be assigned a score of 2 for all timepoints after last assessment. Multiple imputation will be used to impute missing ordinal scores after last assessment for subjects still hospitalized or discharged to hospice, other hospital, or long-term care facility at their last assessment. See Section 6.5.2 for more details.

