Ventilator / ECMO days will be defined as the number of days where the ordinal score > 6 up to and including Study Day 29. The total number of days will be the sum of all reported days, regardless of whether the days occur consecutively or in disjoint intervals. For planned gaps between study days, the day of the qualifying Study Day and the days to the next planned Study Day will be included in the total number of days. The Post-Discharge Supplemental Oxygen CRF questions regarding days of ECMO or invasive ventilation will be used for any time period the subject is not hospitalized at the study hospital. See Section 6.5 for the plan for handling subjects who do not have data through Study Day 29 or die prior to Study Day 29.

Duration of Invasive Mechanical Ventilation/ECMO days will be summarized in a table using medians and quartiles by treatment (Table 38). Bee swarm plots of Invasive Mechanical Ventilation/ECMO days, and days hospitalized by treatment will be generated (Figure 21).

The incidence of new Invasive Mechanical Ventilation/ECMO use will be analyzed by treatment (Table 41). The numerator will only include subjects in category 6 or below at enrollment who change to a category 7 or 8. The denominator will include subjects with a baseline ordinal score of 6 or below. The number of subjects reporting new use of Invasive Mechanical Ventilation/ECMO and the incidence rate along with 95% and 80% CIs estimated using the Blaker method will be reported.

Refer to Table 6 for a list of covariates and subgroup analyses for this endpoint. Refer to Table 7 for imputation methods to be applied to this endpoint.

Proportion of Subjects Alive and Without Respiratory Failure at Study Day 29

The proportion of subjects alive and without respiratory failure at Study Day 29 will be defined as the proportion of subjects with an ordinal score < 7 at any time between Day 26 through Day 32 (Visit window for Study Day 29 Visit). The proportion of subjects with respiratory Failure or death at Day 29 will also be provided. These proportions will be presented by treatment along with 95% and 80% Blaker CIs. Treatment differences will be evaluated using a logistic regression and the p-value will be presented (Table 31).

Refer to Table 6 for a list of covariates and subgroup analyses for this endpoint. Refer to Table 7 for imputation methods to be applied to this endpoint.

Time to Mechanical Ventilation or Death up to and Including Day 29

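### Key secondary survival without respiratory failure through Day 29: invasive ventilation away from the study hospital, begun and ended between contacts, scores as success because the post-discharge oxygen CRF is not named as a source

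*SAP*

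**What the plan says.** Protocol Table 3 (Section 3) defines the endpoint in subjects with a baseline score of 5 or 6 "who did not meet either of the following two categories at any point through Day 29": category 7 (invasive ventilation or ECMO) and category 8 (death). SAP 3.2 restates it as "whether the subject did not satisfy one of the following two categories from the ordinal scale up to and including Study Day 29".

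On the source for ventilation, SAP 4.5 says "invasive mechanical ventilation/extracorporeal membrane oxygenation (ECMO) will be assessed using results of the 8-point ordinal scale". In SAP 8.2.2, incidence of new ventilation/ECMO (Table 41) counts subjects who change to category 7 or 8. SAP 6.5.1 says the time-to-event endpoints, including time to ventilation or death, "will be based on observed ordinal score without imputation along with discharge and death information". The Table 42 shell counts progression to clinical status 7 or 8.

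On frequency, Protocol 8.1.2.1 has clinical status "captured on each study day while hospitalized up until and including Day 29". After discharge, "they will have a study visit on Days 8, 15, 22, 29, and 60 visits". In the notes to the protocol's Schedule of Assessments (Section 1.2), "Day 8, 22 and 60 visits performed by phone call or home visit if discharged from the site hospital", with current status, readmission and mortality asked. SAP 8.2.1 says an ordinal score reflects the prior 24 hours. SAP 3.3.2 does not assign data from unscheduled visits to a time point.

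On the additional source, SAP 8.2.2 states under ventilator/ECMO days: "The Post-Discharge Supplemental Oxygen CRF questions regarding days of ECMO or invasive ventilation will be used for any time period" when the subject is not hospitalized at the study hospital. Parallel sentences appear for oxygen days and for non-invasive ventilation/high-flow days. The CRF is not named in SAP 3.2, in 8.2.1, in the Table 7 rows for this key secondary, or in the Table 30 shell.

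**The concern.** The protocol's endpoint is any-time. The SAP's source for ventilation is continuous only while the subject is in the study hospital; afterwards it is a one-day look about once a week. The SAP fills that gap from the CRF for durations but not for the three event endpoints that rest on the same clinical fact.

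One report could then contradict itself. A subject could contribute ventilator days to Table 38 and still be a success in Table 30, not a new case in Table 41, and censored at Day 29 in Table 42 or 43. A known respiratory failure would be counted as a success in a key secondary endpoint.

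**Working it through.** The documents give no event rate or power for this endpoint, so there is no stated figure to reproduce. The check is a trace of one record and then a coverage calculation.

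**Trace.** Take a subject with baseline score 5, discharged on Day 9 and scored 2 at Day 15. The subject is ventilated at another hospital on Days 16-20, is weaned, scores below 7 at the Day 22 contact, and is home at Day 29.

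| Output | Source named in the SAP | Result |
|---|---|---|
| Ventilator/ECMO days (Table 38) | Ordinal score plus CRF | 5 days |
| Key secondary (Table 30) | Ordinal categories 7 and 8 | Success |
| New ventilation/ECMO (Table 41) | Change to category 7 or 8 | Not a case |
| Time to ventilation or death (Tables 42, 43) | Ordinal score, discharge, death | Censored at Day 29 |

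**Episodes of fixed length.** Assume contacts on Days 15, 22 and 29, one calendar day covered by each score, and start days uniform over Days 9-29 (21 days). An episode of d days (d up to 7) is missed with probability (7 − d)/7:

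- 1 day: 18/21 = 86%
- 3 days: 12/21 = 57%
- 5 days: 6/21 = 29%
- 6 days: 3/21 = 14%
- 7 days or more: 0%

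The SAP Table 1 windows for discharged subjects (6-10, 13-17, 19-25, 26-32) can widen the 6-day gap to 17 − 6 − 1 = 10, 25 − 13 − 1 = 11 or 32 − 19 − 1 = 12 uncovered days. With contacts on Days 13 and 25, a 7-day episode is still missed for 5 of 21 start days (24%).

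**Episodes of random length.** Assume a uniform start within a 7-day interval, exponential duration with mean m, and a score covering the last day of the interval. An episode is missed if it starts and ends within the first 6 days:

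P(missed) = [6 − m(1 − e^(−6/m))] / 7

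| m (days, assumed) | m(1 − e^(−6/m)) | P(missed) |
|---|---|---|
| 5 | 3.494 | 2.506/7 = 36% |
| 7 | 4.029 | 1.971/7 = 28% |
| 10 | 4.512 | 1.488/7 = 21% |
| 14 | 4.880 | 1.120/7 = 16% |

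**Share of subjects.** If 2-4% of subjects are ventilated after leaving the study hospital and survive (assumed), the miscoded share runs from 0.16 × 2% = 0.3% to 0.358 × 4% = 1.4%.

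**Effect on power if misses are equal between arms.** Illustration with 85 subjects per arm and failure rates of 25% versus 15% (all assumed):

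| Failures missed | Power, two-sided 0.05 | Power, two-sided 0.20 |
|---|---|---|
| 0% | 37.0% | 63.7% |
| 2% | 36.2% | 62.9% |
| 5% | 35.0% | 61.8% |
| 10% | 33.2% | 59.8% |

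**The case against.** The strongest reply is that the SAP is silent about the CRF here and does not exclude it. The protocol itself defines failure by ordinal categories, and SAP 8.2.1 and Table 7 speak of progression to respiratory failure or mechanical ventilation as events. Ventilator days are also defined by ordinal score, and there the CRF supplements it, so a programmer might do the same for the key secondary. That is a possible reading. But naming the CRF for the duration endpoints and nowhere else invites the opposite one, and SAP 4.5 points to the scale alone.

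Safeguards exist but do not close the gap. The endpoint review committee may adjudicate key secondary endpoints (SAP 6.5.1, Section 8), but its use is optional and no trigger refers to this CRF. Chart review is for subjects lost to follow-up, and the traced subject completes follow-up. The Master protocol sections on the scale and on readmission, and the MOP, were not supplied; they might define the score as worst status since last contact. Nothing supplied says so.

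Three stronger readings are tempting and not supported:

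- **Transferred inpatients fall in the gap.** Protocol 8.1.2.1 and SAP 4.5 ask for daily scores while hospitalized without naming the study hospital, whereas the schedule note refers to the site hospital. For a subject moved directly to another hospital the text is mixed. The clear case is the discharged subject.
- **The SAP 6.5.1 sentence on time-to-event sources governs the key secondary.** Its list does not include it. For the key secondary the argument rests on SAP 3.2 and 4.5.
- **The missed share is 46%, 37%, 28% and 21%** for means of 5, 7, 10 and 14 days, from 1 − (m/7)(1 − e^(−7/m)). That treats each contact as an instant and ignores the 24-hour look-back in SAP 8.2.1.

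**Conclusion.** The point holds as a gap in the named data source. Followed literally, the SAP does not deliver the protocol's any-time endpoint for subjects discharged from the study hospital, and it lets tables in one report disagree about the same subject.

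The size is small. Death is taken from the SAE form (SAP 4.5) and study-hospital episodes from daily scores, so only survivors ventilated and weaned between contacts are misclassified. About 16% to 36% of such episodes are missed, or 0.3-1.4% of subjects: roughly one subject or fewer in an arm of 100. These figures rest on assumed durations and an assumed 2-4% ventilated after leaving; neither is in the documents. If misses are equal between arms, the power loss is about one point at 2% of failures missed and about four points at 10%.

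A reader might infer a biased odds ratio. A difference between arms in discharge timing could make the misses differential, but nothing in the documents shows such a difference.

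**What to change.** In SAP 3.2, 8.2.1 and Table 7 (key secondary 2 and other secondary efficacy rows 9 and 12), count as an event any invasive ventilation or ECMO through Day 29 recorded by the ordinal score or by the Post-Discharge Supplemental Oxygen CRF. Tables 30, 38, 41, 42 and 43 then agree.

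For time to ventilation or death, use the date on the CRF or the readmission record if there is one. The SAP describes CRF questions about days, and nothing supplied shows that start dates are collected. If only day counts exist, prespecify a dating rule, for example the first day after the last contact without ventilation.

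The cost is a few sentences and one more source in the derivation; the SAP already uses this CRF for ventilator days. The downside is some imprecision in event dates for the few subjects affected.
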